## Appendix E:

# Revised Body Awareness Rating Questionnaire (R-BARQ):

## The Revised Body Awareness Rating Questionnaire

Table 5. Final Revised Body Awareness Rating Questionnaire, With 4-Point Response Scalea

Item Description	Completely Disagree (0)	Somewhat Disagree (1)	Somewhat Agree (2)	Completely Agree (3)
1. I am often tenseb				
2. My body is affected by how I feel b				
3. I am not aware of the way I breathe b				
4. I don't pay attention to the way I move b				
5. I struggle to relax				
6. My body is tense without me knowing why				
7. I try not to show how I'm feeling				
8. My digestion is affected by how I feel b				
9. I can't get comfortable when I'm lying down				
10. My body is unpredictable b				
11. I avoid paying too much attention to my body				
12. I don't like to be touched 				

<sup>oThe items are presented in location order, with easier items on the top and more difficult items on the bottom. bAlso included in the original Body Awareness Rating Questionnaire.

# Appendix F: The Tampa Scale of Kinesiophobia, 11-item version.

# **TSK-11**

This is a list of phrases which other patients have used to express how the view their condition. Please circle the number that best describes how you feel about each statement.

	Strongly Disagree	Somewhat Disagree	Somewhat Agree	Strongly Agree
1. I'm afraid I might injure myself if I exercise.	1	2	3	4
2. If I were to try to overcome my pain, it would increase.	1	2	3	4
3. My body is telling me I have something dangerously wrong.	1	2	3	4
4. People aren't taking my medical condition serious enough.	1	2	3	4
5. My accident/problem has put my body at risk for the rest of my life.	1	2	3	4
6. Pain always means I have injured my body.	1	2	3	4
7. Simply being careful that I do not make any unnecessary movements is the safest thing I can do to prevent my pain from worsening.	1	2	3	4
8. I wouldn't have this much pain if there wasn't something potentially dangerous going on in my body.	1	2	3	4
9. Pain lets me know when to stop exercising so that I don't injure myself.	1	2	3	4
10. I can't do all the things normal people do because it's too easy for me to get injured.	1	2	3	4
11. No one should have to exercise when he/she is in pain.	1	2	3	4

Source: Woby et al. (2005), Psychometric properties of the TSK-11: A shortened version of the Tampa Scale for Kinesiophobia. Pain, 117, 137-144.

## Appendix G: The International Physical Activity Questionnaires (IPAQ) Short Form.

### INTERNATIONAL PHYSICAL ACTIVITY QUESTIONNAIRE

We are interested in finding out about the kinds of physical activities that people do as part of their everyday lives. The questions will ask you about the time you spent being physically active in the last 7 days. Please answer each question even if you do not consider yourself to be an active person. Please think about the activities you do at work, as part of your house and yard work, to get from place to place, and in your spare time for recreation, exercise or sport.

Think about all the **vigorous** activities that you did in the **last 7 days**. **Vigorous** physical activities refer to activities that take hard physical effort and make you breathe much harder than normal. Think *only* about those physical activities that you did for at least 10 minutes at a time.

1.	During the last 7 days , on how many days did you do vigorous physical activities like heavy lifting, digging, aerobics, or fast bicycling?			
	day	rs per week		
	No	vigorous physical activities	→ Skip to question	on 3
2.	How much tir	ne did you usually spend doing vigorc	us physical activities on one of	those days?
		hours per day		
		minutes per day		
	Don'	t know/Not sure		
activi some	ties refer to what harde	e moderate activities that yo activities that take moderate r than normal. Think only ab nutes at a time.	physical effort and make	you breathe
3.	activities li	last 7 days, on how many o ke carrying light loads, bicyc lude walking.	•	
	day	rs per week		
	No	moderate physical activities	→ Skip to question	on 5
4	How much tir	me did you usually spend doing mode	rate physical activities on one of	f those days?

		hours per day
		minutes per day
		Don't know/Not sure
home	, walkii	the time you spent walking in the last 7 days . This includes at work and at ng to travel from place to place, and any other walking that you have done creation, sport, exercise, or leisure.
5.	Durin at a ti	g the last 7 days , on how many days did you walk for at least 10 minutes me?
		_days per week
		No walking Skip to question 7
6.	How m	uch time did you usually spend walking on one of those days?
		hours per day
		minutes per day
		Don't know/Not sure
refer t	o activ	all the gentle exercise that you did in the last 7 days . Gentle activities ities that involve movement or body awareness, but do not make you der than normal. Think only about those physical activities that you did for ninutes at a time.
Pil	ates (i	ne last 7 days , on how many days did you do gentle physical activities like f not included under Moderate Activity, above), Tai Chi, yoga, breathing s or stretching? Do not include walking.
		_days per week
		No gentle physical activities   Skip to question 5
8.	How m	uch time did you usually spend doing gentle physical activities on one of those days?
		hours per day
		minutes per day

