Our primary outcome measures will be a hypermobility-specific functional/disability measure, The Bristol Impact of Hypermobility (BloH) questionnaire.(Palmer, 2017) The BloH is a 55 item questionnaire that asks about pain, fatigue, joint instability, function, self-efficacy and attitudes about having hypermobility. It is the only outcome measure specifically validated for hypermobility-related conditions, and it is recommended by the international Common Data Elements initiative, whose goal is to encourage EDS researchers to use consistent outcome measures.

We will also measure physical activity, to determine whether participation in Pilates allows people to become more active. The International Physical Activity Questionnaire Short Form is a validated survey assessing physical activity during work, sport, and leisure time. (Booth, 2000) We will add questions that will track participation in mind-body exercise, such as Pilates, yoga, Tai Chi, etc. and strengthening, as these activities are not included in the IPAQ.

Kinesiophobia will be assessed through the Tampa Scale of Kinesiophobia, short form (TSK-11), which is an 11-question survey asking about fear of movement and fear of injury. (Woby, 2005) The Tampa Scale of Kinesiophobia is one of the recommended Common Data Elements for EDS. We will also collect qualitative data from weekly electronic contact.

The Revised Body Awareness Rating Questionnaire (R-BARQ) includes 12 questions that ask about body awareness, response to discomfort, breathing patters, and physical response to stress.(Dragesund, 2018) This tool may provide insight into the mechanism by which functional improvements are achieved, by correlating functional improvements with improved body awareness, relaxation, effective breathing, etc.

We will also solicit qualitative feedback about the Pilates program through weekly emails. This qualitative information will build upon a recent study using qualitative methods to assess

attitudes towards exercise among people with hEDS/HSD.(Simmonds, 2017)

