# 3. Objectives and Hypotheses

- 1. Implement a pilot study to assess whether this on-line Pilates course for people with hEDS/HSD results in beneficial changes when compared to a wait-list comparison group. We understand that the evidence will not be strong with a non-random comparison group, but having a comparison group is better than not having one. We hypothesize that 8 weeks of this specialized Pilates training will result in:
  - a. Decreased pain and symptoms, improved function and quality of life (measured using the BloH),
  - b. Increased physical activity (measured using IPAQ with additional questions)
  - c. Improved body awareness (R-BARQ) and less dysfunctional breathing patterns (R-BARQ)
  - d. Decreased fear of movement (TSK-11).
- 2. Pilot test the proposed outcome measurement tools for such a future study. We are looking for basement and ceiling effects, as well as change over time.
- 3. Explore whether certain patterns of implementation of the on-line course are associated with better outcomes. For example, is it better to repeat one module multiple times before moving on, or to move around among modules? This will be descriptive correlational data.
- 4. Gather qualitative data to better understand factors that may influence compliance or maximal benefit. These data can inform future research into either Pilates or use of internet-accessible exercise training for this population. This qualitative information also provides insights into factors that influence participation in exercise within this population, and whether certain patterns are observed among people who benefit from the program compared to those who do not.

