### e. Analysis of outcomes:

- Quantitative data will be coded and entered into Excel, reviewed for outliers, and transferred to SPSS
- Descriptive statistics related to demographics and initial scores for BIoH, IPAQ, TSK-11, R-BARQ
- Descriptive statistics related to subjects use of the different modules (which Pilates modules were used during each of the 8 weeks and overall), and continued use of the modules through the 6 month follow-up.

- Repeated Measures ANOVA comparing pretest, post-test (8 wk) and 6 month after post-test: BIOH, IPAQ, TSK-11, R-BARQ
- ANOVA comparing change over 8 weeks for the Pilates group vs. the wait-list group: BloH, IPAQ, TSK-11, R-BARQ
- Regression analysis using IPAQ, TSK-11, R-BARQ to predict quality of life and function as measured using BloH before intervention, after intervention (including compliance) and 6 months later (including compliance).
- Qualitative analysis of the narrative (email) information using content analysis using the following process:(Bengtsson, 2016)
  - o Decontextualization to identify meaning units, create code list
  - o Recontextualization to verify that all important information has been coded
  - o Categorization to organize themes, with triangulation by investigators
  - Compilation to formulate conclusions, audit, member check if subjects agree

We understand that the lack of a randomized control group makes our current design less rigorous than a randomized control trial (RCT), but having a wait-list comparison group makes the design stronger.

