### Don't know/Not sure

(2): s114-20.

The last question is about the time you spent **sitting** on weekdays during the **last 7 days**. Include time spent at work, at home, while doing course work and during leisure time. This may include time spent sitting at a desk, visiting friends, reading, or sitting or lying down to watch television.

9.	During the last 7 days, how much time did you spend sitting on a week day?	
	hours per day	
	minutes per day	
	Don't know/Not sure	

Items in green are not part of the IPAQ, but were added for purposes of the current study.

Booth, M.L. (2000). Assessment of Physical Activity: An International Perspective. Research Quarterly for Exercise and Sport, 71

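### Appendix G, item 7 lets each respondent report Pilates as Moderate or as Gentle activity, so the IPAQ result for hypothesis 1b depends partly on a label that the plan does not fix

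*Combined protocol and SAP*

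**What the plan says.** Section 2 explains why questions on mind-body exercise and strengthening are added: "as these activities are not included in the IPAQ". Appendix G closes with the note "Items in green are not part of the IPAQ, but were added for purposes of the current study". The Gentle questions 7 and 8 are the mind-body addition. Question 7 lists its examples with a condition on Pilates, "not included under Moderate Activity, above), Tai Chi, yoga, breathing". Moderate Activity is one of the IPAQ's own items.

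The IPAQ categories are graded by effort and breathing together. Vigorous, for example, means "activities that take hard physical effort and make you breathe much harder than normal", and Moderate has the same form one step down. Gentle is defined by breathing no harder than normal.

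Section 3 states hypothesis 1b as "Increased physical activity (measured using IPAQ with additional questions". Section 6e enters the IPAQ in two comparisons, "Repeated Measures ANOVA comparing pretest, post-test (8 wk) and 6 month after post-test: BIOH, IPAQ, TSK-11, R-BARQ" and "ANOVA comparing change over 8 weeks for the Pilates group vs. the wait-list group: BloH, IPAQ, TSK-11, R-BARQ", and uses it as a predictor in the regression. No section says which IPAQ score is meant, how the categories are weighted, or whether Gentle minutes count.

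**The concern.** The condition in question 7 stops one session being counted twice within a survey. It does not make two respondents file the same session in the same place, or make one respondent file it the same way at the next survey. Section 2 treats Pilates as outside the IPAQ, while question 7 accepts that it may already sit inside an IPAQ item.

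Pilates is also the intervention. The label decides whether the assigned sessions themselves appear as a gain in the outcome, and the answer can differ from person to person within the Pilates group. Two people with identical weeks can get different scores, and one person with an unchanged routine can show a change. Leaving out the added items would not cure this, because Pilates filed as Moderate would stay in the score.

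**Working it through.** The plan gives no IPAQ score, standard deviation or effect size, so there is no figure of its own to reproduce. The check asks how far the label can move the result.

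**Inputs from the documents**
- Assigned Pilates: 3 modules of 25 minutes, stated as 75-90 min/week (section 6a). 3 x 25 = 75; reaching 90 needs modules of 90 / 3 = 30 minutes.
- Pilates at entry: at most 30 min/week (section 4b, exclusion vi).
- Group size: 225 in the first group (section 6a) and an equal number on the wait list (section 4e).

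**Assumptions**
- Share of respondents affected by the label: shown as a range.
- SD of 8-week change: 75, 150 or 300 min/week.
- Full adherence to the assigned sessions.

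**Step 1. Effect of a label on one person.** Score shift = minutes moved x (Moderate weight - Gentle weight). Moving from Moderate to Gentle lowers the score; the reverse raises it.

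| Weight gap | 75 min | 90 min |
|---|---|---|
| 0 (equal weights, one total) | 0 | 0 |
| 0.5 | 37.5 | 45 |
| 1 (minutes score, Gentle not counted) | 75 | 90 |
| 2 | 150 | 180 |

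The label is harmless only in the first row. Steps 2 to 4 use a gap of 1.

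**Step 2. Pretest to 8 weeks, Pilates already being done.** Only minutes present at both surveys can be relabelled, so the ceiling is 30 per person. Mean shift if all switching goes one way: 10% x 30 = 3, 20% x 30 = 6, 40% x 30 = 12 min/week.

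**Step 3. At 8 weeks, new study sessions.** These were not done at pretest, so nothing is relabelled, but the label decides whether they enter the score. Mean added to the Pilates group = share filing them as Moderate x 75 to 90. With no other change in activity and 225 per group (two-sided 5%):

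| Share filing as Moderate | Added min/week | SD 75 | SD 150 | SD 300 |
|---|---|---|---|---|
| 0% | 0 | 0 | 0 | 0 |
| 20% | 15-18 | 0.20-0.24 SD; 56-72% | 0.10-0.12 SD; 18-25% | 0.05-0.06 SD; 8-9% |
| 50% | 37.5-45 | 0.50-0.60 SD; about 100% | 0.25-0.30 SD; 76-89% | 0.125-0.15 SD; 26-36% |
| 100% | 75-90 | 1.0-1.2 SD | 0.50-0.60 SD | 0.25-0.30 SD |

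The percentages are the chance of a significant group difference. For scale, 225 per group detects 0.26 SD with 80% power.

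**Step 4. From 8 weeks to 6 months, within group.** Study sessions can now be present at both surveys. Mean shift with one-way switching: 10% gives 7.5-9, 20% gives 15-18, 40% gives 30-36 min/week. These are upper figures, because use during follow-up is encouraged rather than assigned (section 6a).

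**Step 5. With one fixed place for Pilates.** No Pilates minutes reach the Moderate item, so Pilates labelling shifts the score by 0 under any weights. A total of all active minutes is also unaffected by relabelling, but it rises by the assigned 75-90 min/week in the Pilates group at full adherence.

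**The case against.** The strongest reply is that nothing moves if Moderate and Gentle minutes are added with equal weight, and hypothesis 1b does speak of the IPAQ with its added questions. That stands as a condition. The plan suggests that the Gentle items count, but it does not say how.

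The written definitions also separate the two categories, so the choice is a judgement and not wholly free. The protocol describes the exercises as gentle (sections 2 and 7a), so filing them as Moderate may be uncommon. Both points limit the size without removing the problem, because question 7 itself invites the Moderate option.

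Pilates time is asked separately of any intensity label (Appendix C, question 14; Appendix I.2, question 4), and module access is logged. This allows a cross-check, but section 6e does not connect it to IPAQ scoring.

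A reader might infer three stronger things that the documents do not support:
- **Relabelling alone could move the 8-week group comparison by 15-18 min/week at a 20% share.** The entry cap holds that to 6. The larger figure belongs to the classification of new sessions, or to the later within-group comparison.
- **Grading rests on breathlessness, which the course aims to reduce.** The IPAQ categories use effort as well as breathing. Hypothesis 1c concerns dysfunctional breathing patterns measured by the R-BARQ, not breathlessness on exertion.
- **The bias runs against a true benefit.** Labels can move either way, and balanced switching nets to zero.

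**Conclusion.** The point holds in limited form. Question 7 leaves the place of Pilates to each respondent at each survey, and the plan does not state the one scoring rule that would make this harmless. The main consequence at 8 weeks is that an unknown share of the 75-90 min/week of study sessions enters the Moderate item. From 8 weeks to 6 months, label changes can move the score with no change in activity. Relabelling of existing Pilates before 8 weeks is minor: about 6 min/week at an assumed 20%, or 3-12 for 10-40%.

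Whether this matters for significance depends on a change-score SD that the documents do not give. It also depends on adherence and on the share filing Pilates as Moderate. The direction is open. The BIoH is the primary outcome and is unaffected; hypothesis 1b and the IPAQ's role in the regression are affected. This is a cheap improvement to a secondary measure. It also serves objective 2, which is to pilot the measurement tools. In the copy reviewed, the Moderate item's text is partly broken and the green marking is lost, so a further instruction there cannot be excluded.

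**What to change.** 1. **Appendix G, question 7:** delete the parenthetical about Moderate Activity. State there, and in a one-line note at the Moderate item, that all Pilates is reported in the Gentle item only. Limit this to Pilates; leave yoga and Tai Chi to the existing definitions.
2. **Section 6e:** define the IPAQ score. For hypothesis 1b, compare groups on activity excluding Pilates minutes. Vigorous, moderate and walking minutes are then free of Pilates. For the Gentle item, the separate Pilates-minutes questions can be used to take Pilates out, noting that they ask about weekly or typical-week time and not the last 7 days.
3. **Beside it,** show total active minutes including Pilates, by group, as descriptive only, because that total rises by design in the Pilates group.

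The cost is a wording edit to the study's own item, one note and one extra analysis row. Comparability with other IPAQ data falls slightly, and a few people who find Pilates moderately hard will log it as Gentle. Section 4e mentions subjects already enrolled. If pretest surveys were taken with the present wording, record the date of the change, since the edit itself could move up to 30 min/week of pretest Pilates per person between items.

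### Appendix G: the added gentle-activity item sends people who do none back to walking (question 5) instead of forward to sitting (question 9)

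*Combined protocol and SAP*

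**What the plan says.** Appendix G numbers its items 1 to 9. Questions 1, 3, 5 and 7 ask on how many of the last 7 days the person did vigorous activity, moderate activity, walking and gentle activity. Each is followed by a question on time per day, and question 9 asks about weekday sitting.

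The walking item asks "on how many days did you walk for at least 10 minutes", and its none option reads "No walking Skip to question 7". Question 7 is the gentle-activity item, and its none option reads "Skip to question 5". After it come question 8, on time spent on gentle "physical activities on one of those days", and the closing item: "During the last 7 days, how much time did you spend sitting on a week day".

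The form carries the note "Items in green are not part of the IPAQ, but were added for purposes of the current study". Section 2 (Introduction) explains that questions on mind-body exercise were added because the IPAQ does not include them, which identifies the gentle-activity block as one of the additions.

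Section 6a has subjects complete the questionnaires on SurveyMonkey before starting and repeat them at 8 weeks and 6 months. Section 6e uses the IPAQ in the repeated-measures ANOVA, in the regression and in the between-group comparison: "ANOVA comparing change over 8 weeks for the Pilates group vs. the wait-list group: BloH, IPAQ, TSK-11, R-BARQ".

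**The concern.** A skip should carry the respondent past questions that do not apply. This one points backward to a block already completed. Taken literally, it gives a person with no gentle activity no route to the last question.

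The instrument is the measure named for hypothesis 1b (increased physical activity, section 3), and it is repeated at every assessment, so a routing fault could recur in each round. Three kinds of damage are possible: walking answers given a second time and perhaps changed, a missing sitting answer, or a survey left unfinished.

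**Working it through.** No sample-size or error-rate formula applies. The check is a trace of the printed skips in Appendix G.

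**Step 1: compare the four skips.** The shift is the target number minus the item number.

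| Item | Content | Target if none | Shift | Bypasses |
|---|---|---|---|---|
| 1 | Vigorous, days | 3 | 3 − 1 = +2 | 2 (vigorous time) |
| 3 | Moderate, days | 5 | 5 − 3 = +2 | 4 (moderate time) |
| 5 | Walking, days | 7 | 7 − 5 = +2 | 6 (walking time) |
| 7 | Gentle, days | 5 | 5 − 7 = −2 | nothing; goes back |

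The gentle item's position as question 7 is fixed from both sides: the walking skip leads to 7, and the item after the gentle-days question is numbered 8.

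**Step 2: follow the printed path after a none answer at question 7.**

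- No walking: 7 → 5 → 7 → 5, and so on.
- Some walking: 7 → 5 → 6 → 7 → 5, and so on.

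Neither path reaches question 9 unless the person changes the answer at question 7, disregards the instruction, or the live survey is programmed differently.

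**Step 3: apply the form's own pattern.** A shift of +2 from question 7 gives 7 + 2 = 9. The path becomes 7 → 9 → end, and only question 8 (gentle time) is bypassed.

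**Step 4: what can be said about size.** The number of records affected in a survey round is n × p × q. Here n is the number of subjects reaching question 7, p is the share answering none, and q is the share of those who are actually misrouted. The documents give neither p nor q. If the live survey has the right target, q = 0 and nothing is lost. If it enforces the printed target, q = 1 on first reaching the skip and up to n × p records are exposed. The documents do not narrow that range.

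The printed target is the same as that of the moderate item, so a copied line is a plausible cause. That is an inference.

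**The case against.** The strongest reply is that this is a clerical slip in one added item, and that the printed form is not what subjects answer. They use SurveyMonkey, whose branching is not reproduced in the documents, and anyone who tested the none answer would notice an endless loop. A person reading the printed page would also see that the sitting item is introduced as the last one and could simply go on. This stands in part: it means that data loss is unconfirmed. It does not make the printed instruction right, and nothing in the documents corrects it or describes different logic online.

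A reader might go further and infer that the fault biases the comparison of Pilates with wait-list. The argument would be that none is the usual answer at baseline, remains usual in the wait-list group at 8 weeks and becomes rare after Pilates. The documents do not support this, for four reasons.

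- The eligibility criteria (section 4b) exclude recent movement-based therapy, but they admit people who continue exercises learned from it and allow up to 30 minutes/week of Pilates. The gentle item also counts stretching and breathing work. The criteria therefore do not show that none is a common answer, and no share at baseline or 8 weeks is given.
- No IPAQ scoring rule is stated, so it is not known whether sitting enters the outcome for hypothesis 1b.
- The vigorous, moderate and walking answers are all given before question 7, and the none answer is itself recorded. Bias in those activity items would require walking answers to be changed on a second pass, or whole records to be lost.
- The form of the damage depends on the software. A loop that cannot be left yields an unfinished survey; one that can be left may still lead to question 9. A count of lost sitting values cannot be assumed.

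**Conclusion.** The point holds as a minor but definite error in an outcome instrument. The none option of question 7 has the wrong target: it is the only one of four skips that goes backward, and followed literally it never leads to question 9. Repeated walking answers, missing sitting data and unfinished surveys are risks that depend on the live survey, or the respondent, following the print.

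The size of any loss, and whether it differs by group or over time, cannot be established from the documents. A claim of differential bias in the activity comparison would go beyond them. The IPAQ is a secondary measure. The BIoH is a separate questionnaire (Appendix D), and its items are not themselves affected.

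**What to change.** 1. In Appendix G, change the target of the none option at question 7 from question 5 to question 9.
2. In the live SurveyMonkey form, test the none path at question 7, both with and without walking, and confirm that each ends at question 9.
3. If any surveys were collected with the faulty routing, report how many were affected, by group and time point. Use the first walking answer where it is recoverable.

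The cost is one changed digit and a short branching test. The third step adds a count from the survey export, needed only if the live form carried the error. Design, sample size and the planned analyses do not change.
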